**Setting:** For **Phase 1 and Phase 2**, recruitment and enrollment will take place either in person with partner schools and organizations or remotely either in partnership with schools that have agreed to collaborate with us, or through study advertisements placed on social media. Given our ability to play the videogame and collect data remotely, we are seeking additional partnerships with schools nationwide and recruiting participants individually through social media, including Facebook and Instagram. For Phase 1 (focus groups), recruitment may also take place online through social media platforms, including Facebook and Instagram. Focus groups will take place online through Zoom where participants will be able to see and interact with each other.

Of note, the Principal Investigator, [name] will not be involved in any aspects of consenting participants or their parents, the randomization process, data collection or direct performance of data analysis procedures.

**Participants:** For **both phases**, participants must be Black heterosexual adolescent girls aged 14 to 18 and currently enrolled in high school. For **Phase 2**, participants must also: 1) be able to participate in web-based videogame (willing to sit for 60-minutes/session to play the game); 2) not have been tested for HIV in the past year; and, 3) be able to provide assent/parental/guardian consent.

**Phase 1: Conduct focus groups and playtesting with Black adolescent girls and develop *InvestiDate*** (30 participants): Focus group discussions with Black adolescent girls will inform the new version of the game by providing ideas for content and gameplay around HIV/STI testing, condom use, and sexual risk taking. We have used and refined this iterative process for current videogame projects. Data collected will be used to inform the development of the multiplayer videogame, *InvestiDate*. Example question for the focus groups include, “What are some red flags that teens your age look for when considering dating someone?”, “What are some green flags that teens your age look for when considering dating someone?”, “What might make it difficult for teens your age to get tested for HIV/STIs?”

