risk behaviors (such as alcohol use) can result in HIV/STI. Additionally, participants may also recognize that they have risked acquiring HIV/STI and may have already acquired these diseases without knowing by confirmatory testing. It also involves interactions with the participants' peers. The assessments and instruments may also present a potential risk given that some of the questions are sensitive in nature and address issues around sexual activity and other risky behaviors.

11. **Minimizing Risks:** Describe the manner in which the above-mentioned risks will be minimized.

A number of precautions will be actively integrated into the research procedures to protect the confidentiality and anonymity of all participants. For participating in Yale's videoconferencing tool, Zoom, participants will be asked to find a secure, private setting, free from others outside the study that may overhear the discussion. All research staff and the staff and volunteers participating in the intervention will be required to complete training in research ethics. Data collection forms will be designated by ID numbers only. A separate master file of names, addresses, contact persons, and telephone numbers, along with the study ID numbers will be maintained in a locked file cabinet in the research team's offices. All data entry and analyses will be completed with ID numbers only. The study will be explained to others, such as the guardian/parent and program staff as a study of child development that will focus on promoting healthy behaviors. In instances in which data are requested from other sources or it is beneficial to the participant to provide information to another individual or agency (e.g. medical personnel) this will only be done with the written permission of the guardian/parent on a "Release of Information" form stipulating who the information is provided to, or received from. The research staff will follow standard confidentiality procedures for research programs.

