from the project director/research assistant with details about the study and exclusion/inclusion criteria. If the participant is under 18, the research staff member will email the parental information sheet to the parent and contact them by email or phone to obtain written consent. If either the participant or the parent do not wish to be in the study or have their child participate in the study, no further contact will be made. Participants that meet the requirements and after consent or parent permission and assent have been obtained, will be enrolled in the study by the project director/research assistant. For focus groups, participants will also be recruited through the use of social media sites, including Facebook and Instagram. Participants will be asked to click on a link in the ad, which will take them to the Yale Qualtrics webpage where they will fill out a form with basic demographic information (age, race) and their contact information (email and phone number) and parental contact information (email and phone number) if the participant is under 18. If participants meet eligibility criteria, a research staff member will email the potential participant the focus group information sheet for them to review and set up a time to contact them by phone to review the study and obtain verbal consent. If the participant wishes to participate in the study and is under 18, the research staff member will email the parental information sheet to the parent and contact them by phone to obtain verbal consent. If either the participant or the parent do not wish to be in the study or have their child participate in the study, no further contact will be made. Focus groups will take place through Zoom where participants will be able to see and interact with each other.

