Participation in this study will be strictly voluntary, confidential and non-discriminatory. The study will be advertised via posters and flyers located at partner schools and through emails sent directly to students and announcements made during class. The study will also be advertised through social media, including Facebook and Instagram. Potential participants will fill out an eligibility survey through the Yale Qualtrics webpage where they will provide basic demographic information (age, race, sexual orientation) and their contact information (email and phone number) and parental contact information (email and phone number) if the participant is under 18. If participants meet eligibility criteria, a research staff member will email the potential participant the study information sheet for them to review and set up a time to contact them by phone or zoom to review the study and obtain verbal consent. If the participant wishes to participate in the study and is under 18, the research staff member will email the parental information sheet to the parent and contact them by email to obtain written consent. We will provide, via email, the adolescents and their parents with an age-appropriate description of the study and told about what they might expect. In describing the study to the participant, the purpose of the study will be described as "finding out how teens can make choices that are healthier for them". In describing the study to the guardian/parent, we will indicate that the study will focus on promoting healthy behaviors in adolescence and on providing strategies to assist adolescents in making decisions about the many challenges they face; particularly as they relate to risky behaviors, including sex. For the focus groups we will employ waived signature of consent. Parents who do not wish for their children to participate will contact the project director. For the evaluation, we will obtain informed written assent from the participant and written informed consent from their guardian/parent. For both phases, if a participant or their guardian/parent indicates that they do not wish to participate, there will be no further involvement in the study. We will also obtain agreement from the appropriate administrator at the participating program.

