In some cases, we may conduct focus groups through Yale's video conferencing service, Zoom. To obtain verbal consent, the Research Assistant will discuss the study with their guardian/parent and obtain verbal assent from the participant and verbal consent from their guardian/parent. At the beginning of the Zoom meeting, participants will be provided with an age-appropriate description of the study and told about what they might expect. In describing the study to the participant, the purpose of the study will be described as "finding out how kids can make choices that are healthier for them". In describing the study to the guardian/parent, we will indicate that the study will focus on promoting healthy behaviors in adolescence and on providing strategies to assist adolescents in making decisions about the many challenges they face; particularly as they relate to health relationships and dating. If a participant or their guardian/parent indicates that they do not wish to participate, there will be no further involvement in the study. We will work with our study partners to identify potential participants; study partners will email our approved flyer to those that may fit within our study inclusion criteria (black teen girls aged 14-18). Participants that are interested in participating in the focus groups may reach us through the phone number or email listed on the approved flyer.

7. **Evaluation of Subject(s) Capacity to Provide Informed Consent/Assent:** Indicate how the personnel obtaining consent will assess the potential subject's ability and capacity to consent to the research being proposed.

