This research does not involve subjects with limited decision-making capacity. Parents and adolescents will be provided with an age-appropriate description of the study and told about what they might expect. In describing the study to the participant, the purpose of the study will be described as "finding out how kids can make choices that are healthier for them". In describing the study to the guardian/parent, we will indicate that the study will focus on promoting healthy behaviors in adolescence and on providing strategies to assist adolescents in making decisions about the many challenges they face; particularly as they relate to risky behaviors, including sex. For focus groups, we will employ waived signature of consent. Parents who do not wish for their children to participate will contact the project director. For the pilot randomized controlled trial, we will obtain informed written assent from the participant and written informed consent from their guardian/parent.

8. **Non-English Speaking Subjects:** Explain provisions in place to ensure comprehension for research involving non-English speaking subjects. If enrollment of these subjects is anticipated, translated copies of all consent materials must be submitted for approval prior to use.

Non-English Speaking Subjects will not be able to participate in this project.

As a limited alternative to the above requirement, will you use the short form\* for consenting process if you unexpectedly encounter a non-English speaking individual interested in study participation and the translation of the long form is not possible prior to intended enrollment? YES  NO

**Note\*** If more than 2 study participants are enrolled using a short form translated into the same language, then the full consent form should be translated into that language for use the next time a subject speaking that language is to be enrolled.

Several translated short form templates are available on the HRPP website (yale.edu/hrpp) and translated HIPAA Research Authorization Forms are available on the HIPAA website (hipaa.yale.edu). If the translation of the short form is not available on our website, then the translated short form needs to be submitted to the IRB office for approval via modification prior to enrolling the subject. ***Please review the guidance and presentation on use of the short form available on the HRPP website.***

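### The protocol gives conflicting instructions on what parents of minors are told and on how their permission is obtained

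*Combined protocol and SAP*

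**What the plan says.** **What parents are told.** Section I, item 11 (Minimizing Risks) says: "The study will be explained to others, such as the guardian/parent and program staff as a study of child development", with healthy behaviors as its focus. Section III, item 3 (Recruitment Procedures), the opening of item 6 (Process of Consent/Assent) and item 7 (capacity to consent) instead tell parents that the study helps adolescents make decisions, "particularly as they relate to risky behaviors, including sex". The Zoom focus-group paragraph in item 6 uses the same script with a different ending: "particularly as they relate to health relationships and dating".

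**How focus-group permission is obtained.** In Section III, item 3, if a girl recruited for a focus group is under 18, "the research staff member will email the parental information sheet to the parent and contact them by phone to obtain verbal consent". Item 6 repeats this in its social-media paragraph, and its Zoom paragraph also calls for verbal parental consent with verbal assent. But the opening of item 6, and item 7, waive the signature for focus groups and then add: "Parents who do not wish for their children to participate will contact the project director".

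**How trial permission is obtained.** Items 3, 6 (opening) and 7 of Section III require written parental consent. The social-media paragraph of item 6, however, opens by covering both phases and then describes verbal parental consent by phone.

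**The concern.** Participants are girls aged 14 to 18. The focus groups are meant to inform the game by "providing ideas for content and gameplay around HIV/STI testing, condom use, and sexual risk taking", and Table 1 asks trial participants about intercourse, condom use and HIV/STI testing. A parent told only about child development, or only about relationships and dating, has not been told the subject matter. If the opt-out sentence is applied as it reads, silence would count as permission for a focus group. If the social-media paragraph is applied as it reads, a trial participant could enter on a parent's spoken agreement when other sections require it in writing. The protocol is the document that staff follow and the IRB approves, so it should not support two answers to any of these questions.

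**Working it through.** No formula applies. The check is to set the current passages side by side.

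**1. Description given to parents**

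| Place | Applies to | Sex named? |
|---|---|---|
| Section I, item 11 | not limited to a phase | No |
| Section III, item 6, Zoom paragraph | focus groups on Zoom | No |
| Section III, item 3 | recruitment | Yes |
| Section III, item 6, opening | both phases | Yes |
| Section III, item 7 | both phases | Yes |

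Two places omit sex and three name it. None of the five names HIV/STI testing. The Zoom paragraph is not marginal. It begins as a provision for some cases, but the Setting text in Section I, item 4 and two paragraphs of Section III say that focus groups will be held on Zoom, so its script could cover most or all of them.

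**2. Permission for focus groups**

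| Place | Rule |
|---|---|
| Section III, item 3, focus-group text | Staff obtain the parent's verbal consent |
| Section III, item 6, social-media paragraph | Same |
| Section III, item 6, Zoom paragraph | Same, with verbal assent |
| Section III, item 6, opening | Signature waived; objecting parents make contact |
| Section III, item 7 | Same as the line above |

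Three places require an affirmative answer and two can be read as opt-out. The waiver does not settle the matter. Section III, item 9 ties the waiver of signed consent to focus-group participation, and waiving a signature removes the signature, not the permission. The justification for a full waiver of consent is left as template text. The checkbox marks in item 9 are not legible in the review copy, so which boxes were ticked cannot be confirmed.

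Number affected (Section I, item 4): four focus groups of five and two playtesting groups of five, 4 × 5 + 2 × 5 = 30. This is a ceiling, because 18-year-olds are eligible and need no parental permission.

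**3. Permission for the trial**

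Three places (items 3, 6 opening and 7) require written parental consent. One (the item 6 social-media paragraph) covers both phases but has staff "email the parental information sheet to the parent and contact them by phone to obtain verbal consent". That paragraph also refers to the focus-group information sheet and closes with the focus groups on Zoom, so its body looks like the focus-group procedure under an opening that is too broad. Read literally, it still contradicts the written rule for trial participants under 18 who are recruited through social media. The documents do not say how many that would be.

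**The case against.** The strongest reply is that these sentences only summarize how the study is introduced. Section III, items 3 and 6 say that parents of minors are emailed an information sheet, and that sheet may disclose the sexual content in full. This stands as a limit on the conclusion: nobody reading the protocol alone can say that parents will be uninformed. It does not excuse the protocol from giving staff conflicting scripts, and the Zoom paragraph itself mentions no sheet.

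Second, the sentence in Section I, item 11 sits among confidentiality precautions and concerns explaining the study to others; it is not the consent procedure. That is fair, but the sentence names the guardian or parent.

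Third, the sentence read here as opt-out may only offer parents a way to decline. That reading is possible, since the opening of item 6 also has staff contact the parent of a minor to obtain consent. But where the sentence appears, it is the only parental step named after the focus-group waiver, and it is followed by a contrasting statement that the trial needs written consent. The ambiguity remains.

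A reader might also infer that minors can enter the randomized trial with no parental permission. The documents do not support this. Written parental consent is stated three times for the trial, and Section I, item 8 makes consent an eligibility condition. For the trial, the issues are what the parent is told and whether a verbal route has been left open by mistake.

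**Conclusion.** The concern holds as three inconsistencies in the current text: the parent description (two places against three), the focus-group permission rule (three against two, at most 30 participants and fewer under 18), and one paragraph whose verbal consent contradicts the written rule for the trial. The consequence is a risk, not a certainty, of less informed or presumed permission. It depends on which passage staff follow and on the content of information sheets and consent forms that were not reviewed.

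Two stronger inferences should be resisted.

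- A reader might expect parents to discover the topic after allocation and withdraw girls unevenly from the *InvestiDate* arm. The documents do not support that. Table 1 puts the same sexual-behavior and testing questions to both arms at baseline and at months 1 and 4, and partner testing enters the randomization algorithm, so that item at least must be collected before allocation. Only the game content differs between arms, and no parental withdrawal rate is given.
- A reader might take HIV/STI testing to be the main outcome that parents are not told about. The protocol names no primary outcome. The aims list acceptability and feasibility first, the data analysis text tests participant and partner testing, and Section V hypothesizes condom use and partner testing. Testing is worth naming to parents because it is a subject of the study, not because of its rank as an outcome.

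**What to change.** Four edits to the protocol and scripts:

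1. Section I, item 11: remove the guardian/parent from the neutral description, and keep that description for program staff and bystanders, where it protects confidentiality.
2. Section III, item 6, Zoom paragraph: replace the parent description with the one already used in item 3, the opening of item 6 and item 7. Preferably that common text should also name HIV/STI testing. It should agree with the information sheet.
3. Section III, item 6 (opening) and item 7: delete the sentence about objecting parents, or restate it as an additional way to decline. State documented verbal parental consent as the single rule for focus groups and playtesting.
4. Section III, item 6, social-media paragraph: limit verbal consent to focus groups, so that written parental consent governs the trial without exception.

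The cost is a wording amendment and matching changes to scripts. The downside is that some parents may decline before enrollment once the subject is stated plainly.

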**Table 1: Assessments**

Assessment	Base-line	Month 1	Month 4
Participant Demographics (i.e. gender, age, education)	X		
HIV/STI Testing Rates and Partner HIV/STI Testing Rates	X	X	X
Sexual Risk Behaviors—Self-reported measures of sexual intercourse with/without condoms 	X	X	X
Vulnerability to Risky Sexual Behaviors 	X	X	X
Risk Behaviors Associated with HIV/STIs - Youth Risk Behavior Survey 	X	X	X
HIV Knowledge (HIV-KQ)  (45 item true/false questionnaire)	X	X	X
STI Knowledge (STD-KQ)  (27-item true/false questionnaire)	X	X	X
Subjective Norms 	X	X	X
Intentions 	X	X	X
Attitudes—Multi-dimensional Condom Attitudes Scale (MCAS) 	X	X	X
Self-efficacy in sexual risk behaviors—Sexual Risk Behavior Beliefs and Self-efficacy (SRBBS) Scales 	X	X	X
Condom Self-Efficacy (CUSES)  (28-item Likert scale)	X	X	X
Sexual Communication 	X	X	X
*Satisfaction with game play/acceptability and feasibility (12-item Likert scale) 		X	

5. **Genetic Testing** N/A

6. **Subject Population:** Provide a detailed description of the types of human subjects who will be recruited into this study.

Adolescents ages 14-18 will be recruited into this study.

7. **Subject classification:** Check off all classifications of subjects that will be specifically recruited for enrollment in the research project. Will subjects who may require additional safeguards or other considerations be enrolled in the study? If so, identify the population of subjects requiring special safeguards and provide a justification for their involvement.

- |  |  |  |
|--|--|--|
|  Children   |  Healthy                |  Fetal material, placenta, or dead fetus |
|  Non-English Speaking  |  Prisoners                         |  Economically disadvantaged persons      |
|  Decisionally Impaired |  Employees                         |  Pregnant women and/or fetuses           |
|  Yale Students         |  Females of childbearing potential |  |

NOTE: Is this research proposal designed to enroll children who are wards of the state as potential subjects?

Yes  No

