8. **Inclusion/Exclusion Criteria:** What are the criteria used to determine subject inclusion or exclusion?

Inclusion/exclusion criteria: For **both phases**, participants must be Black heterosexual adolescent girls aged 14 to 18 and currently enrolled in high school. For **Phase 2**, participants must also: 1) be able to participate in web-based videogame (willing to sit for 60-minutes/session to play the game); 2) not have been tested for HIV in the past year; and, 3) be able to provide assent/parental/guardian consent.

9. How will **eligibility** be determined, and by whom?

Eligibility will be determined by the research team. If a prospective participant meets the inclusion criteria, they will be eligible to participate in the project.

10. **Risks:** Describe the reasonably foreseeable risks, including risks to subject privacy, discomforts, or inconveniences associated with subjects participating in the research.

The potential risks associated with this study have to do with maintenance of the confidentiality of the identities of the participants enrolled in the study and information relating to them. For focus groups, we will address the risk to confidentiality to participants that are participating in the study and that this cannot be guaranteed given that others will also be participating. However, participants will be told that they should not disclose information about other participants and all participants should respect the privacy of each other. Only participants' ID numbers will be recorded on the electronic assessments themselves to protect confidentiality. Sensitive data is encrypted in transit and in storage. The web data-entry interface allows data entry to be performed from anywhere on the Internet and uses 128-bit secure sockets layer (SSL) security to protect the confidentiality of the data. Playing *InvestiDate* may pose a potential psychological risk in that we address sensitive issues around sexual activity and how HIV/STI is transmitted, and the specifics of how certain

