The research assistant will be available at all times to provide assistance to the participants, answer their questions, and serve as a resource if any distress or concern arises. The research assistant will be available to assist the participants, the community sites staff, and the research staff member administering the assessments if there appears to be any distress around the questions being asked. If participants need additional or more intensive attention, the research assistant will contact [name], our clinical psychologist on the team, who will consult with the team in order to potentially provide consultation resources to the participant.

12. **Data and Safety Monitoring Plan:** Include an appropriate Data and Safety Monitoring Plan (DSMP) based on the investigator's risk assessment stated below. (Note: the HIC will make the final determination of the risk to subjects.)

- a. What is the investigator's assessment of the overall risk level for subjects participating in this study? Minimal risk
- b. If children are involved, what is the investigator's assessment of the overall risk level for the children participating in this study? Minimal risk
- c. Include an appropriate Data and Safety Monitoring Plan. Examples of DSMPs are available here <http://your.yale.edu/policies-procedures/forms/420-fr-01-data-and-safety-monitoring-plans-templates> for
  - i. Minimal risk
  - ii. Greater than minimal

The principal investigator is responsible for monitoring the data, assuring protocol compliance, and conducting the safety reviews quarterly. During the review process, the research team will evaluate whether the study should continue unchanged, require modification/amendment, or close to enrollment.

The principal investigator or the Human Investigative Committee (HIC) have the authority to stop or suspend the study or require modifications.

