This protocol presents minimal risks to the subjects and Unanticipated Problems Involving Risks to Subjects or Others (UPIRSOs), including adverse events, are not anticipated. In the unlikely event that such events occur, Reportable Adverse Events (which are events that are serious or life-threatening and unanticipated (or anticipated but occurring with a greater frequency than expected) and possibly, probably, or definitely related) or Unanticipated Problems Involving Risks to Subjects or Others that may require a temporary or permanent interruption of study activities will be reported immediately (if possible), followed by a written report within 5 calendar days of the Principal Investigator becoming aware of the event to the IRB via the RNI submission process in IRES IRB and any appropriate funding and regulatory agencies. The investigator will apprise fellow investigators and study personnel of all adverse events that occur during the conduct of this research project through regular study meetings and via email as they are reviewed by the principal investigator. We will use procedures to detect and respond to adverse events that ensure prompt discovery of any adverse events and to minimize their effects. There is adequate surveillance and protections to discover adverse events promptly and keep their effects minimal. Data and safety monitoring procedures in this study include collection and monitoring of paper-based questionnaires and an organizational structure of clearly defined tasks assigned to all research personnel involved in the conduct of this study. We will keep a thorough record of research activities and completion of scheduled assessments.

We have established a Data Safety and Monitoring Board (DSMB) composed of two experts, [name] and [name], in clinical trials in young teens and in statistical analysis of clinical trials to oversee the safety and data integrity of this study. DSMB will also review the progress of the study.

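### The harms the protocol foresees are not systematically asked about in either arm, and no harm summary by arm is planned, so a low or zero harm count would be weak evidence

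*Combined protocol and SAP*

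**What the plan says.** Section I, item 10 (Risks) names confidentiality first. It then says that playing InvestiDate "may pose a potential psychological risk in that we address sensitive issues around sexual activity", and that "participants may also recognize that they have risked acquiring HIV/STI and may have already acquired these diseases without knowing". On the group format it adds "It also involves interactions with the participants' peers". It also lists the sensitive survey questions, which both arms answer, as a risk.

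Table 1 (Section I, item 4) sets out what is collected at baseline, month 1 and month 4. No row is labelled distress, confidentiality breach or adverse event. The nearest is "Satisfaction with game play/acceptability and feasibility (12-item Likert scale", at month 1 only. A vulnerability measure at all three visits is listed with the risk-behaviour measures. Section IV, item 2 plans data on the experience of the game for intervention participants, directly after the intervention.

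Item 11 (Minimizing Risks) has a research assistant on hand to "serve as a resource if any distress or concern arises", with the team psychologist as the next step. Item 12 (Data and Safety Monitoring Plan) provides quarterly safety reviews by the principal investigator and a two-member DSMB. It includes the claim "There is adequate surveillance and protections to discover adverse events promptly and keep their effects minimal". Reportable adverse events are related "events that are serious or life-threatening and unanticipated (or anticipated but occurring with a greater frequency than expected". Unanticipated problems that may interrupt the study are also reportable. All adverse events are to be shared with study personnel.

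The statistical text plans comparisons on HIV/STI testing and partner testing. It mentions no harm outcome.

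**The concern.** A pilot in 14-18-year-olds is meant to show whether the intervention is acceptable and feasible and to inform a full-scale trial. Part of that evidence is whether the foreseen harms occurred and how often. If nobody is asked, the recorded count depends on who happened to notice or volunteer something. A short list of events, or an empty one, could then be read as evidence of safety when it partly reflects how events were gathered.

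The comparison between arms has the same weakness. The control game has no sexual-health content, while both arms answer the same sensitive questions. Asking both arms the same thing would help separate the effect of the game from that of the surveys. The plan does not use the shared surveys for this, and its only post-game experience data come from one arm.

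**Working it through.** The documents give no harm rate, expected frequency or harm sample size, so there is no stated figure to reproduce. The check has two parts.

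**1. Named risks against the means of finding them**

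| Risk (item 10) | Visible row in Table 1 that asks about it | Other route |
|---|---|---|
| Distress from the game | None; satisfaction scale at month 1 | Research assistant; experience data, intervention arm only |
| Realising one may be infected | None as a harm; vulnerability listed as a study measure | Research assistant |
| Peer interaction | None | Research assistant |
| Sensitive questions, both arms | None | Staff, if distress is apparent |

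Play totals 2 to 4 hours and may be by Zoom. Follow-up runs to four months. Worry about infection, or trouble with a co-player, can arise after staff contact ends.

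Three statements in item 12 also do not sit well with the rest of the protocol:
- It says adverse events are not anticipated, whereas item 10 anticipates several harms.
- It allows anticipated events to be reported when they exceed an expected frequency, but gives none, so that clause cannot be applied.
- It names paper questionnaires as a monitoring procedure. Item 4 and Section IV, item 2 have assessments entered in Qualtrics, although Section IV, item 4 also mentions storing paper assessments.

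**2. Scale (illustration; rates and capture are assumptions)**

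Input from the protocol: n = 40 per arm. Let r be the true proportion of girls with an event and s the proportion of events that are captured. With independent participants, P(no event recorded) = (1 − r·s)^40.

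| True rate r | s = 90% | s = 50% | s = 25% | s = 10% |
|---|---|---|---|---|
| 5% | 16% | 36% | 60% | 82% |
| 10% | 2% | 13% | 36% | 67% |
| 20% | 0.04% | 1.5% | 13% | 45% |

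For example, at r = 10% and s = 25%, 0.975^40 = 0.363. At s = 90%, 0.91^40 = 0.023.

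The exact two-sided 95% upper limit for 0/40 is 1 − 0.025^(1/40) = 8.8%. That limit applies to the recorded rate r·s. For the true rate it becomes 8.8%/s: 9.8% at 90% capture, 17.6% at 50% and 35% at 25%.

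For the comparison, take true rates of 5% and 25%, two-sided alpha 0.05, and equal capture in both arms. With both rates multiplied by s, power = Φ{[Δ − 1.96·√(2p̄(1−p̄)/40)] / √[(p1(1−p1)+p2(1−p2))/40]}. This gives 71%, 39%, 21% and 11% at s = 100%, 50%, 25% and 10%. Even with full capture, 5% against 15% has only 32% power. These values are approximate at such small counts. All figures in this part ignore play-group clustering and dropout. Positive correlation within groups would raise the chance of recording no event.

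**The case against.** The strongest reply is that the protocol does have a safety system. Staff are on hand, distress during assessments is covered, there is a route to a psychologist, reviews are quarterly, a DSMB exists and all adverse events are shared with personnel. The study is assessed as minimal risk and its efficacy analyses are exploratory. All of this stands, and it rules out four stronger readings:

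- **That the named harms cannot be detected.** Passive detection finds some events. In the illustration, a 36% chance of recording none is a 64% chance of recording at least one. The limit is that review and DSMB oversight act only on events someone has captured. The principal investigator, who conducts the reviews, takes no part in data collection (item 4, Setting).
- **That the reporting definition excludes these harms.** It governs external reporting and does not restrict what staff may notice. Serious related distress can qualify, and a breach that may interrupt the study can qualify as an unanticipated problem. Only non-serious distress or worry is clearly left out.
- **That peer disclosure is a named harm of the trial.** The explicit disclosure wording concerns the focus groups. For the game, the text says only that peers interact. Trial participants do play in fixed groups, so a question about it is reasonable, but this is an inference.
- **That no comparison is possible.** Volunteered events could be tabulated by arm. Ascertainment could differ between arms, so the comparison would not be reliable.

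The individual questionnaire items are not reproduced, and some text after the safety plan was not available. Absence can be claimed only for the visible text. The experience data might also bring out upset, but only in one arm and only directly after play.

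**Conclusion.** The point holds in limited form. On the visible text, the foreseen harms are not systematically elicited in either arm and no summary by arm is planned. The adequacy of surveillance is asserted without being shown. A low or zero count would be weak evidence, and harms could not be reliably compared.

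How weak depends on capture, which is unknown. Across the assumed range, at a true rate of 10%, the chance of an empty record runs from 2% to 67%. No single value should be quoted as an estimate, since the rates, capture and independence are all assumptions. The gap does not invalidate the trial or its efficacy analyses. It is a worthwhile, inexpensive improvement, best made before the follow-up surveys are fielded.

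**What to change.** Add a row to Table 1 for study-related harms at month 1 and month 4, in the existing Qualtrics surveys, worded identically in both arms. About three yes/no items with a free-text line would do:

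1. Upset or worried because of the game or the questions.
2. Something said or done in the group was shared outside it.
3. Other problems from taking part.

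Month 4 matters because the month-1 survey follows directly after play and would miss later events.

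Log every occurrence, including those noticed by staff, with its source. Add to the analysis text a descriptive tabulation by arm with exact confidence intervals, given to the DSMB. With 40 per arm it should not be presented as a test of safety.

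Reconcile item 12 with items 4 and 10 and Section IV: whether adverse events are anticipated, and whether the monitoring questionnaires are paper or online. Either state the expected frequency the reporting clause relies on or say that none is available.

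Costs: a protocol amendment, about one minute on each of two surveys, staff time to review responses when submitted, and a less favourable adverse-event count than passive reporting would give.
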